14.2.4 Safety Analysis

Extent of Exposure – Duration (number of cycles/infusions) of decitabine doses (cumulative and intensity) will be summarized.

Adverse Events - All adverse events will be coded using NCI CTCAE v. 4.0. The incidence of treatment-emergent adverse events (number and percent of patients reporting the adverse event at least once during the study) will be summarized. In addition, adverse events will be summarized by investigator attribution of relationship to study medication and by grade. Similar summaries will be provided by treatment cycle.

Clinical Laboratory Evaluation – Applicable laboratory parameters will be graded according to NCI CTCAE version 4.0. The incidence of maximum grade (number and percent of patients experiencing the maximum grade during the study) will be summarized for each laboratory parameter. Similar summaries will be provided by treatment cycle. Graphical displays of select hematological parameters will also be provided.

Vital Signs, Physical Findings, and Other Safety Observations – Vital signs, findings from physical examinations, ECOG scores and weights will be presented in listing format.

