3.0 PATIENT SELECTION

3.1 Inclusion Criteria

One of the following:

- Patient must have non-M3 AML and be ≥ 60 years of age OR
- non-M3 AML with relapsed disease OR
- Symptomatic MDS with one of the following:
 - Symptomatic anemia with either hemoglobin < 10.0 g/dL or requiring RBC transfusion
 - Thrombocytopenia with a history of two or more platelet counts $< 50,000$ /mcL or a significant hemorrhage requiring platelet transfusions
 - Neutropenia with two or more ANC $< 1,000$ /mcL

All of the following:

1. Patient must have an ECOG performance status ≤ 2 .
2. Patient must have $>10\%$ disease burden measured by cytomorphology, flow cytometry, or cytogenetics.
3. Patient must have peripheral white blood cell count $\leq 50,000$ /mcl.
4. Patient must have adequate organ function, defined as:
 - a. Total bilirubin ≤ 1.5 x ULN
 - b. AST/ALT ≤ 2.5 x ULN
 - c. Serum creatinine ≤ 2.0 x ULN
5. Patient must have undergone ≤ 2 cycles of prior hypomethylating agent (decitabine or azacitidine).
6. Patient must be enrolled in HRPO# 201011766 (“Tissue Acquisition for Analysis of Genetic Progression Factors in Hematologic Diseases”).
7. Patient must be ≥ 18 years of age.
8. Patient must be able to understand and willing to sign an IRB-approved written informed consent document.

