6.1 Delay for Cytopenia or Infection

As cytopenias are a defining feature of AML and MDS, their presence alone does not generally warrant dose modifications or delays. Patients will receive four cycles of therapy without adjustment for any cytopenia. Following Cycle 4, dose modifications or delays for cytopenias will be made at the discretion of the investigator.

Patients with febrile neutropenia (temperature $\geq 38.5^\circ$ with ANC $< 1,000/\mu\text{l}$) or systemic infections should have treatment held until clinical resolution of the infection.

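### The hematology toxicity table takes the maximum grade during the study without reference to baseline, so cytopenia present at entry inflates the grade 3–4 rates

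*Combined protocol and SAP*

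**What the plan says.** The laboratory paragraph of 14.2.4 sets the scale: "Applicable laboratory parameters will be graded according to NCI CTCAE version 4.0". It then fixes the statistic: "The incidence of maximum grade (number and percent of patients experiencing the maximum grade during the study) will be summarized for each laboratory parameter". By-cycle versions are also planned, and "Graphical displays of select hematological parameters will also be provided".

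The adverse event paragraph just above it is worded differently: "The incidence of treatment-emergent adverse events (number and percent of patients reporting the adverse event at least once during the study) will be summarized". That qualifier is not defined, and it is not carried over to the laboratory paragraph. The same laboratory text stands in 12.2.4 of the earlier protocol versions in the file.

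In 3.1, each of the three MDS routes is a cytopenia:
- "Symptomatic anemia with either hemoglobin" below 10.0 g/dL, or a need for red cell transfusion;
- "Thrombocytopenia with a history of two or more platelet counts" below 50,000/mcL, or a significant hemorrhage requiring platelet transfusions;
- "Neutropenia with two or more ANC" below 1,000/mcL.

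The AML routes carry no count criterion, but 6.1 covers both diseases: "As cytopenias are a defining feature of AML and MDS". A blood count is taken at baseline within 7 days before the first dose (5.2.2), on Day 1 of each cycle (5.2.3), and weekly, with the option of every other week after Cycle 1 (5.2.7).

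**The concern.** A maximum over the study is a fair toxicity summary when patients start near normal. Here many can be expected to start with the abnormality being counted. The worst on-study grade then mixes two things: the grade the patient brought in, and any worsening after treatment began. A patient whose counts never move, or who is low at the first count and then recovers, is tabulated in the same cell as one whose counts fell after dosing.

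This matters because myelosuppression is the toxicity of most interest. It is the reason 6.3 gives for reducing the schedule after response, and 6.1 has four cycles given without adjustment for cytopenia. Readers will take the hematology grade table as a description of what the 10-day schedule does to blood counts.

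**Working it through.** The plan states no figure for this summary, so there is nothing to reproduce. The check is a reading of the rule, followed by an illustration of its size.

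**Inputs**
- Statistic: maximum grade per parameter, overall and by cycle, with no baseline term (14.2.4).
- Scale: CTCAE v4.0 (10.1, 14.2.4). The cut-offs are not printed. I assume that a neutrophil count below 1,000 and platelets below 50,000 lie at the grade 3 boundary, and that hemoglobin just under 10 g/dL without transfusion is a lower grade.
- Enrollment: 25 + 100 = 125 patients (14.3).
- b, the share who enter at grade 3 or higher and are still there at the first on-study count: not given; assumed 0.2 to 0.8.
- t, the incidence of new grade 3–4 among patients below grade 3 at entry: not given; assumed 0 to 50%.

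**Step 1: what the rule does to one patient.** The maximum over the study cannot be lower than the grade at the first on-study count. If that count is no better than at entry, the maximum is at least the entry grade. This holds wherever the cut-offs lie and whatever happens later. Cycle 1 of the by-cycle summary carries the entry grade in the same way, and later cycles do so for as long as the cytopenia persists.

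**Step 2: what it does to the table.** All of the share b are counted, plus the fraction t of the remaining 1 − b:

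reported = b + (1 − b)t

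excess over t = b + (1 − b)t − t = b(1 − t)

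Reported grade 3–4 incidence, with the excess in percentage points in brackets:

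| b | t = 0 | t = 25% | t = 50% |
|---|---|---|---|
| 0.2 | 20% (20) | 40% (15) | 60% (10) |
| 0.4 | 40% (40) | 55% (30) | 70% (20) |
| 0.6 | 60% (60) | 70% (45) | 80% (30) |
| 0.8 | 80% (80) | 85% (60) | 90% (40) |

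In the t = 0 column, 125 × b gives 25, 50, 75 and 100 patients in the grade 3–4 cell with no new toxicity.

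**Step 3: what is lost.** The reported rate moves with t at slope 1 − b. At b = 0.6, a rise in t from 0 to 50% moves the reported figure only from 60% to 80%: a 50-point difference shows as 0.4 × 50 = 20 points.

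**The case against.** The strongest case against is that this is one descriptive table among several. The same section plans treatment-emergent adverse events, with attribution, grade and cycle. The adverse event definition in 10.1 is broad enough for a worsened count to be recorded and attributed there. No objective in 2.0 concerns safety, schedule reduction under 6.3 is triggered by response and not by laboratory grades, and a shift table could be produced at reporting because the baseline count exists. In a single-arm study a shift table also cannot tell drug effect from progressing disease, since progression lowers counts too.

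Much of this stands, and it limits the point. It means a reader should not infer that the plan leaves nothing to say about tolerability. It also does not extend to all laboratory toxicity: entry limits in 3.1 (bilirubin 1.5, AST/ALT 2.5 and creatinine 2.0 times the upper limit of normal) cap the baseline abnormality for those tests, so their maximum grade stays informative.

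It does not remove the point for hematology. The adverse event qualifier is undefined and does not govern the laboratory table. The graphs cover selected parameters with no baseline rule. That a better table could be made later is a reason to specify it now, because the table that is specified gives an inflated hematology rate.

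**Conclusion.** The concern holds for the hematology parameters. The stated summary carries entry grade into the on-study toxicity rate, and nothing in the documents available corrects it. The direction is certain whenever some patients are still at grade 3 or higher at the first on-study count and not all of the others reach that level. The size is not derivable: 20 to 80 points at t = 0 and 10 to 40 points at t = 50% are illustrations that rest on assumed b, assumed t and assumed CTCAE cut-offs.

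A reader might go further and infer that grade 3–4 rates will be close to universal regardless of the drug. The documents do not support that. They give no distribution of entry grades. AML patients need no cytopenia to qualify. The platelet criterion is historical, so a patient may be above the threshold at first dose, and the anemia route can be met at what is assumed to be a lower grade.

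**What to change.** Keep the maximum-grade table and add to 14.2.4, for each hematology parameter:
- a shift table of baseline grade (from the 5.2.2 evaluation) by worst post-baseline grade, overall and by cycle;
- the incidence of new or worsened grade 3–4, with the denominator stated as patients below that grade at baseline: those below grade 3 for reaching grade 3 or higher, and those below grade 4 for reaching grade 4;
- a separate listing of patients already at grade 4 at baseline, who cannot worsen on the scale.

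No new visits or samples are needed, since the baseline count is already required within 7 days of first dose. The cost is extra table programming and a smaller denominator for the incidence figures. The text should also say what the addition does not do: it removes carried-over baseline grade, but does not by itself separate drug effect from disease progression in a single-arm study.

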14.2.5 Description of Planned Subgroup Analyses

The following subgroups (if sufficient numbers of patients) will be explored with respect to the primary and overall survival endpoints.

- Age (60-69 years old vs ≥ 70 years old)
- Cytogenetics
- Patients with AML-associated mutations in *DNMT3A*, *TET2*, *IDH1*, or *IDH2* vs those who do not have somatic variants in these genes.

14.3 Sample Size

We anticipate initially enrolling 25 patients at Washington University. Once we establish a routine exome analysis with validation and calculation of the rate of patient-specific mutation clearance, we will enroll an additional 100 patients from at least 2 additional centers.

15.0 DATA SUBMISSION SCHEDULE

Case Report Form	Submission Schedule
Original Consent Form	Prior to registration
Patient Registration Form Disease Diagnosis Form Inclusion Criteria Worksheet Exclusion Criteria Worksheet	Prior to starting treatment
Treatment Record Form	To be maintained throughout a patient's treatment cycle. The complete record is due at completion of treatment.
Bone Marrow Sample Collection Form	To be maintained throughout the course of the study at designated bone marrow sample collections time points (See Appendix 2).
Pathology: Bone Marrow Biopsy	To be completed upon the return of pathology report for each bone marrow biopsy.
Study Calendar Form	To be completed with the date of each time point upon occurrence.
Labs Form	To be completed upon the return of laboratory reports for each study time point (See Appendix 2)
Dose Modifications	To be maintained throughout the course of the study if dose modifications are performed.
Therapy Response Form	To be filled out upon remission (prior to, and/or on therapy)
End of Study Form	Due at the completion of the EOS visit, at the time of death, and/or at the time that the patient is lost to follow-up
Follow Up Form	
 • 30 days post date of last decitabine dose. • Every 6 months for 2 years after the last dose of study drug.
Record of Adverse Events	At the time of any AE

Any queries generated by Washington University must be responded to within 28 days of receipt by the participating site. The Washington University research team will conduct a regular review of data status at all secondary sites, with appropriate corrective action to be requested as needed.

Appendix 1 ECOG Performance Scale

Activity Status	Description
0	Asymptomatic, fully active, and able to carry on all predisease performance without restrictions.
1	Symptomatic, fully ambulatory but restricted in physically strenuous activity and able to carry out performance of a light or sedentary nature, eg, light housework, office work.
2	Symptomatic, ambulatory and capable of all self-care but unable to carry out any work activities. Up and about more than 50% of waking hours: in bed less than 50% of day.
3	Symptomatic, capable of only limited self-care, confined to bed or chair more than 50% of waking hours, but not bedridden.
4	Completely disabled. Cannot carry on any self-care. Totally bedridden.
5	Dead

Appendix 2 Study Flow Chart

Study Flow Chart

Test	Pre-study ¹	Base-line ²	All Cycles Day 1	All Cycles Days 1-10 ³	Cycle 1 Day 4 ± 1	Cycle 1 Day 10 ± 1 and 28 ± 4	Every week	Every 2 weeks	Even cycles Day 28±4	End of Study
Informed Consent	X									
Medical History		X								
Physical Exam		X ^a	X ^b							X
Transfusion Requirements ^c		X ^c	Ongoing							
Bone Marrow Aspirate and Biopsy	X ^d					X ^d			X ^d	X ^d
Flow Cytometry ^c	X									
Peripheral blood for correlative studies					X					
Pregnancy test		X								
CBC with differential and platelets		X	X				X ^f			X
Serum Chemistries ^g		X	X					X ^f		X
Decitabine administration ^h				X						
Adverse Events			Ongoing							
Post-study follow-up										X ⁱ

¹ To be performed within 14 days of the first dose of decitabine.

² To be performed within 7 days of the first dose of decitabine.

³ Decitabine may be reduced to Days 1-5 or Days 1-3. See Section 6.3 for details.

^a To include height, weight, and ECOG.

^b To include weight.

^c Care should be given to record the frequency of transfusions from 8 weeks prior to first dose of study drug through the duration of the study.

^d Bone marrow biopsy and aspirate should be performed at baseline, at Cycle 1 Day 10 ± 1, and at Day 28 ± 4 of Cycles 1, 2, 4 and 6 for clinical disease assessment. Patients who achieve with clinical response (CRi or better) and are receiving cycles every 6 weeks, will undergo bone marrow biopsies on day 42 ± 4. Following Cycle 6, bone marrow biopsies should be performed at the discretion of the treating physician to assess for relapse or progression. Standard bone marrow procurement procedures will be followed for collection of the tissue. To include: correlative studies (collected under HRPO# 201011766), morphologic assessment, cytogenetics and FISH at all time points. A skin biopsy sample (collected under HRPO# 201011766) is required at pre-study, but may have been collected months or even years prior to first dose of decitabine.

^e On bone marrow or peripheral blood.

^f After Cycle 1, these labs may be obtained every other week (CBC) or once a month (Chemistries) at the discretion of the treating physician.

^g Serum chemistries include bicarbonate, calcium, glucose, total protein, albumin, BUN, potassium, chloride, sodium, creatinine, total bilirubin, AST, ALT, alkaline phosphatase, and LDH.

^h Decitabine treatment will be 20 mg/m² over a 1-hour IV infusion on consecutive Days 1-10 every 28-day cycle. The dose will be calculated based on actual patient weight at the beginning of each cycle. Patients may be premedicated with lorazepam, prochlorperazine, palonosetron, or ondansetron at the treating physician's discretion.

ⁱ Patients will be followed for 30 days following the date of the last decitabine dose to monitor for toxicity, survival and response. Thereafter, the investigator or designee will record information on subsequent therapy, disease progression, and death, every 6 months for 2 years after first dose of study drug or until the patient is lost to follow-up.

The information contained in this document is regarded as confidential and, except to the extent necessary to obtain informed consent, may not be disclosed to another party unless law or regulations require such disclosure. Persons to whom the information is disclosed must be informed that the information is confidential and may not be further disclosed by them.

Study Schema:

Patients with progressive disease after two cycles (defined as a clear increase in bone marrow blast count, typically a $> 50\%$ increase in bone marrow blasts over baseline) should be removed from study.

Patients with stable disease may continue on study and should undergo a diagnostic bone marrow biopsy at the end of even numbered cycles.

Once AML patients achieve morphologic complete remission with incomplete blood count recovery (CRi) or MDS patients achieve a marrow complete response (Marrow CR) as defined in Section 9.0, decitabine administration may be decreased to five consecutive days to limit myelosuppressive toxicity at the discretion of the treating physician. After two cycles of five consecutive days of treatment, if the patient meets the definition of CR with complete cytogenetic response as defined in Section 9.0, administration may further be decreased to three consecutive days per cycle at the discretion of the treating physician.

Sample collection for correlative studies:

Bone marrow biopsies should be performed at baseline, at Cycle 1 Day 10 ± 1 , and at Day 28 ± 4 of Cycles 1, 2, 4, and 6. Following Cycle 6, bone marrow biopsies should be performed at the discretion of the treating physician to assess for relapse or progression.

Peripheral blood samples should be collected on Day 4 ± 1 of Cycle 1. Collection should be obtained 45 ± 15 minutes after decitabine infusion is initiated.

Genomic Predictors of Decitabine Response in AML/MDS

Table of Contents

Section	Page
1.0 INTRODUCTION	6
1.1 Rationale.....	6
1.2 Decitabine and Hypomethylating agents in AML/MDS.....	8
1.2.1 Pharmacokinetics and Metabolism of Decitabine.....	10
1.2.2 Experience with extended dosing schedules.....	11
1.3 Correlative Studies	12
2.0 OBJECTIVES.....	14
2.1 Primary Objective.....	14
2.2 Secondary Objectives	14
3.0 PATIENT SELECTION.....	15
3.1 Inclusion Criteria	15
3.2 Exclusion Criteria.....	15
3.3 Inclusion of Women and Minorities.....	16
4.0 REGISTRATION PROCEDURES	17
4.1 Confirmation of Patient Eligibility.....	17

1.0 INTRODUCTION

1.1 Rationale

Personalized therapy for cancer requires that 1) patient-specific factors (e.g. patient-specific mutations, expression profiles, or pharmacogenomics) influence treatment algorithms, and 2) once therapy is initiated, *in vivo* responsiveness is used to guide further therapy. The modern era of genomics has provided significant insights into cancer pathogenesis by describing patterns of germline and somatic variants, as well as defining disease-specific patterns of gene expression. However, the application and integration of this data with therapeutics remains a difficult task.

Decitabine is a commonly used single-agent therapy for patients with acute myeloid leukemia (AML) and/or myelodysplastic syndrome (MDS). Historically, it has yielded clinical complete responses in approximately 25% of patients across diverse clinical trials, it is well tolerated, and it can be given as in the outpatient setting. However, the majority of patients do not respond to decitabine, the molecular etiology of decitabine sensitivity is unknown, and there are no algorithms to predict patient responsiveness *a priori* or even within one month of starting therapy.

AML and MDS are two closely related hematological disorders characterized by ineffective hematopoiesis and malignant expansion of clonal myeloid cells. Both AML and MDS frequently occur in elderly patients and some cases are secondary and/or related to long-term bone marrow damage after radiation or chemotherapy. Current therapy for AML consists of cytotoxic chemotherapy followed by consolidation chemotherapy or stem cell transplantation. Using these approaches, current cure rates may be as high as 60% for patients younger than 60 with good risk cytogenetics (e.g. t(15;17), t(8;21), inv(16)).[4] Outcomes in patients ≥ 60 years old and with relapsed disease remain poor with 2 year survival of only ~25%.[5] Historically, the available treatment for MDS has been symptomatic and has not been shown to be effective in producing sustained improvement in hematopoiesis or in delaying leukemic evolution[6, 7].

Current AML therapy is poorly tolerated in elderly and pre-treated patients due to hematologic and non-hematologic toxicities; following such therapy, patients typically require 3-4 weeks of hospitalization for treatment of neutropenic fevers and for regular transfusions. Even among the relatively healthy patients enrolled in clinical trials, induction mortality in the elderly can be as high as 20-40% following standard induction therapy,[8-11] and moderate to severe non-hematologic toxicity occurs in at least an additional 30% of patients.[9, 12-14] Consequently, many older AML patients are not offered traditional intensive chemotherapy, but receive supportive care alone.[15] More effective and less toxic therapies are needed to provide durable remissions in a significant proportion of elderly AML in populations.

[REDACTED]

[REDACTED]

[REDACTED]

[REDACTED]

We and others have recently used whole genome sequencing to identify recurrent, somatic mutations in AML and MDS patients in four genes that are involved in methylcytosine regulation: *DNMT3A*, *IDH1*, *IDH2*, and *TET2*. [29-37] Collectively, nearly half of all AML/MDS patients have a mutation in one of these four genes. *DNMT3A* mutations are associated with an adverse outcome in AML patients treated with cytotoxic chemotherapy. [35, 38] However, it is not yet clear whether the presence of mutations in one or more of these genes is associated with response or resistance to decitabine.

Genomic Predictors of Decitabine Response in AML/MDS

In this study, we will treat patients with the current state-of-the-art decitabine schedule.[3] We will perform exome sequencing on all patients and correlate response with mutation status, rate of mutation clearance, expression profile, plasma decitabine levels, and DNA methylcytosine content reduction. This approach will comprehensively assess genomic and pharmacologic parameters that could clinically predict patient response to decitabine.

In this study, we will combine analysis of patients with AML and MDS. Recent genomic analysis has shown that AML and MDS have shared mutations in many of the same genes, shared patterns of mutation acquisition, and shared patterns of mutation evolution.[39, 40] Furthermore, MDS, like AML, presents with clonal hematopoiesis, even when the morphologic blast count is zero.[36] Because this study will identify and track the rate of clearance of patient specific mutations, and because decitabine has been shown to have efficacy in both AML and MDS patients, [2, 3, 16-19, 41-45] combining analysis of AML and MDS patients is reasonable. Asymptomatic MDS patients are excluded because these patients are typically followed with watchful-waiting rather than with chemotherapy.

[REDACTED]

[REDACTED]

[REDACTED]

Genomic Predictors of Decitabine Response in AML/MDS

[REDACTED]

[REDACTED]

[REDACTED]	[REDACTED]	[REDACTED]	[REDACTED]	[REDACTED]
[REDACTED]	[REDACTED]	[REDACTED]	[REDACTED]	[REDACTED]
[REDACTED]	[REDACTED]	[REDACTED]	[REDACTED]	[REDACTED]
	[REDACTED]	[REDACTED]	[REDACTED]	[REDACTED]
	[REDACTED]	[REDACTED]	[REDACTED]	[REDACTED]
	[REDACTED]	[REDACTED]	[REDACTED]	[REDACTED]
	[REDACTED]	[REDACTED]	[REDACTED]	[REDACTED]
[REDACTED]	[REDACTED]	[REDACTED]	[REDACTED]	[REDACTED]
	[REDACTED]	[REDACTED]	[REDACTED]	[REDACTED]
	[REDACTED]	[REDACTED]	[REDACTED]	[REDACTED]
[REDACTED]	[REDACTED]	[REDACTED]	[REDACTED]	[REDACTED]
[REDACTED]	[REDACTED]	[REDACTED]	[REDACTED]	[REDACTED]
[REDACTED]	[REDACTED]	[REDACTED]	[REDACTED]	[REDACTED]

[REDACTED]

[REDACTED]

Genomic Predictors of Decitabine Response in AML/MDS

[Redacted text block]

[Redacted text block]

[Redacted text block]

[Redacted text block]

[Redacted text block]

[Redacted text block]

[Redacted text block]

Genomic Predictors of Decitabine Response in AML/MDS

[REDACTED]

[REDACTED]

[REDACTED]

[figure not shown]
[REDACTED]	[REDACTED]	[REDACTED]
[REDACTED]	[REDACTED]	[REDACTED]
[REDACTED]	[REDACTED]	[REDACTED]
[REDACTED]	[REDACTED]	[REDACTED]
[REDACTED]	[REDACTED]	[REDACTED]
[REDACTED]	[REDACTED]	[REDACTED]
[REDACTED]	[REDACTED]	[REDACTED]
[REDACTED]	[REDACTED]	[REDACTED]
[REDACTED]	[REDACTED]	[REDACTED]
[REDACTED]	[REDACTED]	[REDACTED]

[REDACTED]

[REDACTED]

[REDACTED]

[REDACTED]

